##### Subjects initially assigned to placebo:

- can enter the Open-label Phase only if the DMC allows it, as outlined above.
- can enter the Open-label Phase even if they have discontinued the double-blind phase, but were compliant with the protocol 48 weeks post Dose 1 Day 1, and continue their participation in the Post-treatment Follow-up Period until the time of unblinding. can stay in the Open-label Phase until all subjects initially assigned to luspatercept complete the total treatment duration of 5 years from subjects' Dose 1 Day 1 in the treatment period of this ACE-536-B-THAL-001 study or discontinue earlier.
- at the time of unblinding, placebo subjects who discontinued treatment and continued their participation in the Post-treatment Follow-up Period until the time of unblinding

will have the opportunity to enter the Open-label Phase, if they still fulfill the following main eligibility criteria, prior to receiving their first dose of luspatercept:

- Inclusion criteria: numbers 6 and 8 (Refer to Section 4.2);
- Exclusion criteria: numbers “1-10, 15-17 and 21” (Refer to Section 4.3)

Per Investigator’s request, subjects who discontinue luspatercept in the double-blind Treatment Period for reasons not related to subject’s safety, and are still in the Post-treatment Follow-up Period at the time of unblinding, may access the Open-label Phase and be re-treated with luspatercept after consultation with Sponsor Medical Monitor and review of safety and efficacy data as long as they still fulfill the above eligibility criteria prior to Dose 1 Day 1.

**Note:** Subjects who discontinue from the study before the unblinding and without completing the PTFP period are not allowed to re-enter this study and access luspatercept in the Open-label Phase.

Subjects will be discontinued from study as appropriate, for reasons listed in Section 11.

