-  LTTP will end when all subjects completed 48 weeks of double-blind treatment or discontinued before reaching 48 weeks double-blind treatment, whichever is the earlier date, or at the time the study is unblinded (per DMC recommendation). Only subjects that do not discontinue for reasons as described in Section 11 can enter in the LTTP.
-  Only for subject who discontinue prior to completion of 48 weeks in the double-blind Treatment Period.
-  End of Study visit can occur at any time up to at least 156 weeks post last dose.
-  HCV-RNA test and HBsAg and/or HBVDNA .
-  +/- 10 day window around for MRI assessments and DXA is allowed (MRI for LIC, myocardial iron, spleen and LVEF). These assessments to be performed as indicated on specified week, regardless of dose delays. MRIs and DXA scans performed within the 4 weeks prior to the ICF signature can be accepted, if subject does not show any relevant clinical symptoms judged by the Investigator as sufficient reason to repeat these procedures within the Screening/Run-in period and agreed with the Sponsor.
-  Placebo subject who discontinued the study, but were compliant with the protocol 48 weeks post Dose 1 Day 1, and continued their participation in the Post-treatment Follow-up Period until the time of unblinding, refer to Section 3.1.4.
-  For all subjects on treatment at the time of Open-label Phase initiation, continue with the appropriate dose number.
-  For subjects who have documented diagnosis of  $\beta$ -thalassemia in their medical history, by other methodology or do not have a source laboratory report in the medical files, the  $\beta$ -thalassemia genotype can be done at any time during the course of the study.
-  The same Cardiac Doppler Echocardiography technique should be used within a subject throughout the study duration.
-  As per standard of care.
-  Follow-up visits at Weeks 9, 24, 48, 72, 96, 120, 144 and 156 post last dose should be performed by all subjects, regardless if a subject has Early Discontinued or not.
-  For early discontinuation subjects, these parameters to be reported up to 48 weeks Post Dose 1 Day 1 or Week 9 post last dose whichever is the later date.

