### 6.4. Open-label Phase

During the Open-label Phase, the following evaluations will be performed at the frequency specified in the Table of Events, [Table 3](#). The evaluations should be performed prior to dosing on the visit day, as applicable, unless otherwise specified. An administrative visit window of  $\pm 5$  days is permitted.

**Only subjects who, at the time of unblinding, are in Post-treatment Follow-Up and are on placebo, will perform the following assessments and procedures in addition to the procedures and assessments that will be performed by subjects who are continuing the treatment with luspatercept after the unblinding of the study:**

- Assessment of eligibility (only subjects who are in the Post-treatment Follow-up who were treated with placebo during the double-blind treatment and discontinued the IP). Inclusion criteria numbers 6 and 7 and exclusion criteria numbers 1-10, 15-17 and 21 must be met at Dose 1 Day 1
- Iron chelating therapies: including type of iron chelating therapy, period of treatment (ie, dates) and dose changes 24 weeks prior to Dose 1 Day 1 with luspatercept in the Open label Phase and record on ongoing basis (as detailed in Section 6.1).

- Prior medications/therapies: 24 weeks prior to Dose 1 Day 1 of luspatercept
- Prior procedures 24 weeks prior to Dose 1 Day 1 of luspatercept
- Transfusion assessment – 24 weeks RBC transfusion history prior to Dose 1 Day 1 of the Open-label Phase of luspatercept including Hb levels prior to each transfusion, the number of units and or volumes transfused, and the dates of transfusion. If available, the Hct of the transfused unit should be collected, as well as the age when the subject started regular transfusion. These retrospective data will be recorded in the subject's electronic case report form (eCRF).
- Serum ferritin: 24 weeks prior to Dose 1 Day 1 of luspatercept.
- ECOG performance status ([Appendix B](#))
- 12-Lead Electrocardiogram – read locally
- Females: Serum medically supervised pregnancy test with a minimum sensitivity of 25 mIU/mL for FCBP at Day 1 Dose 1 of luspatercept
- Serum chemistry (as detailed in [Section 6.1](#))
- Urinalysis: microalbumin, creatinine, microalbumin/creatinine (as detailed in [Section 6.1](#))

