### 8.1. Permitted Concomitant Medications and Procedures

#### 8.1.1. General Concomitant Medication Usage

During screening and throughout the study subjects may take stable doses of medications for chronic conditions that are not specifically excluded by the protocol (see Section 4.3 Exclusion Criteria).

The Investigator should consult the medical monitor regarding any questions about whether a new medication or dosage of existing medication would require the patient to discontinue from the study.

All concomitant treatments, used from 12 weeks prior to first dose of IP until the End of Study visit must be reported on the eCRF.

All prior and concomitant blood and blood products received, iron chelating and antihypertensive therapies used from 24 weeks prior to first dose of IP until the End of Study visit must be reported on the eCRF.

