### 9.6.3.10. Transfusion Independence

Transfusion independence is defined as the absence of any transfusion during any consecutive “rolling” 8-week time interval within the treatment period, ie, Days 1 to 56, Days 2 to 57 and so on. Subjects discontinued from double-blind treatment for lack of therapeutic effect or with less than 56 days of assessment during the double-blind treatment period will be counted as non-responders. The number and percent of subjects who achieve transfusion independence (defined as at least 8 weeks transfusion-free) will be compared between the two treatment groups. The Cochran Mantel-Haenszel (CMH) test with stratification factor as strata would be performed with randomization factors as strata, corresponding 95% CI associated with the test will be provided.

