10. EFFICACY ANALYSIS

All efficacy evaluations are conducted using the ITT population, with the exception of Quality of Life analyses that are conducted on the HRQoL evaluable population. Statistical comparisons are made between luspatercept plus BSC vs. placebo plus BSC. Key secondary efficacy results are considered statistically significant after consideration of the strategy for controlling the family-wise Type 1 error rate, as described in Section 10.1, Multiplicity. All statistical tests are 2-sided at the significance level of $\alpha = 0.05$, and the corresponding p-values and 2-sided CIs for point estimates are reported, unless specified otherwise.

For the early treatment discontinued subjects, i.e., patients who did not complete 24 weeks or 48 weeks of double-blinded treatment period, the transfusion records were collected up to 48 weeks or 9 weeks post last dose, whichever was the later date. All the transfusion records collected throughout the entire study period up to the efficacy cutoff date were used in the RBC related efficacy analyses. The efficacy cutoff date for the primary CSR was defined as the minimum date among death date, study discontinuation date, last dose date + 20, and 11MAY2018. For the primary and key secondary endpoints, if at the time of data summary, a subject's efficacy cutoff date was before the end of the 12-week interval or a subject had any invalid transfusion records (i.e., transfusion unit not available) during the specified 12-week interval, this subject was included in the analysis as a non-responder.

All the efficacy analysis for the final CSR will not include the assessments for the placebo patients who crossed over to luspatercept. In other words, the assessments for the placebo patients will be analyzed up to the cross-over timepoint. For those subjects in the original luspatercept treatment, their assessments will be analyzed until the new efficacy cutoff date which is defined as the minimum date among death date, study discontinuation date, last dose date + 20.

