10.5.9 Transfusion Independence

The number and percent of subjects who achieve transfusion independence will be summarized by treatment group and the treatment comparison will be analyzed using the CMH model stratified by the geographical regions defined at randomization. Transfusion independence is defined as the absence of any transfusion during any consecutive “rolling” 6-week, or 8-week or 12-week time interval within the entire study period up to the efficacy cutoff date, i.e., Day 2 to 43, Day 3 to 44, ..., Day x to efficacy cutoff date for 6-week interval (or Day 2 to 57, Day 3 to 58, ..., Day x to efficacy cutoff date for 8-week interval, or Day 2 to 85, Day 3 to 86, ..., Day x to efficacy cutoff date for 12-week interval). Subjects whose efficacy cutoff date that is before day 43 (for 6-week based), or day 57 (for 8-week based) or day 85 (for 12-week based) will be counted as non-responders.

The duration of transfusion independence will be summarized by the Kaplan–Meier method. The median duration of response, 25th and 75th quartiles with the associated 2-sided (at 0.05 alpha level) 95% CIs will be presented for each treatment group. The min and max of duration will be provided

for all responders. The Kaplan-Meier plots of the transfusion independence duration, defined as time from first response to end of response (see below) will also be provided. Only subjects who achieve a response will be included in the analysis.

The duration of transfusion independence will be calculated similar to the duration of erythroid response, which is defined as Last Day of Response – First Day of Response +1,

where

First Day of Response = the first day of the first 6-week (or 8-week or 12-week) interval when the subject meets response,

Last Day of Response = the last day of the last 6-week (or 8-week or 12-week) interval when the subject meets response.

For subjects who continue to respond at the efficacy cutoff date, the end day of the response will be censored at the date of efficacy cutoff and the duration of response will be calculated as date of efficacy cutoff – first day of response +1, where date of efficacy cutoff is defined in Section 10.

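### Rolling transfusion endpoints in the final CSR can count weeks in which transfusions were not being collected as transfusion-free, for subjects who stopped double-blind treatment and later entered the Open-label Phase

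*SAP*

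**What the plan says.** **Analysis window.** SAP 10.5.9 defines transfusion independence as no transfusion in any rolling 6-, 8- or 12-week "time interval within the entire study period up to the efficacy cutoff date". SAP 10.5.1 (rolling response) and 10.5.7 (response duration) use the same span. SAP 10.5.10 models transfusion frequency in successive 12-week intervals and overall. For the final CSR, SAP Section 10 says that "the assessments for the placebo patients will be analyzed up to the cross-over timepoint". For subjects originally on luspatercept, the cutoff is the earliest of death, study discontinuation and last dose + 20 days. It does not say which treatment course the last dose belongs to.

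**Collection.** Under Protocol Table 3, footnote 24, transfusion data for early stoppers are "reported up to 48 weeks Post Dose 1 Day 1 or Week 9 post last dose whichever is the later date". SAP Section 10 describes the same limit as what was done. Protocol 6.6 lists only adverse events and malignancy at follow-up visits from Week 24 after last dose. Protocol 6.4 asks for "24 weeks RBC transfusion history prior to Dose 1 Day 1 of the Open-label Phase of luspatercept", but only from placebo subjects who enter from follow-up.

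**Missing data.** SAP Section 10 and 10.7 make a subject a non-responder if the cutoff precedes the end of the interval or if a transfusion record lacks its unit count. SAP 10.5.9 adds only a minimum cutoff day.

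**Protocol definition.** Protocol 9.6.3.10 confines independence to any rolling "8-week time interval within the treatment period" and counts those who stop for lack of therapeutic effect as non-responders.

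**The concern.** A week without collection produces no transfusion record. Neither non-responder rule catches it, because no record is invalid and the cutoff lies later. Such a week contributes zero units to a rolling sum and satisfies the independence definition.

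The primary CSR avoided this. Its cutoff could not run past last dose + 20 days, which lies inside the 63 days of collection after last dose. In the final CSR, the time between stopping and open-label entry can fall inside the window for anyone who came back. SAP 4.1 says that discontinued placebo subjects could do so.

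Subjects were eligible only if they had no transfusion-free period above 35 days, so an apparently empty 42-day stretch off drug would more plausibly be missing data than benefit. At stake are extended secondary analyses reported with CMH p-values, odds ratios, Kaplan-Meier durations and negative binomial p-values.

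**Working it through.** The plan gives no figure for this gap. Its window lengths reproduce: Day 2 to 43 is 42 days, Day 2 to 57 is 56 days, and Day 2 to 85 is 84 days.

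**Inputs**
- D: first dose date.
- E, end of scheduled collection: the later of D + 336 days (Week 48) and last dose + 63 days (Table 3, footnote 24). E is Week 48 if the last dose was by Week 39 (48 − 9). A later stop moves E later and shortens the gap.
- Retrospective history: 168 days before open-label Dose 1, placebo subjects from follow-up only (Protocol 6.4).
- U, open-label entry: not given. SAP Section 2 dates the primary SAP 19 June 2018, before the primary lock. SAP 15.1 ties unblinding to that lock, and Protocol 3.1.4 starts the Open-label Phase after unblinding. I take U = 19 June 2018 as the earliest date; later entry lengthens the gap. The primary data cutoff, 11 May 2018, is shown for comparison.

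**Uncollected days**
- Placebo: U − E − 168.
- Luspatercept, if any were re-treated: U − E.

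A window of w days is wholly blank when this is at least w. With E at Week 48, the latest first dose is U − 336 − 168 − w for placebo and U − 336 − w for luspatercept.

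| Window | Placebo, U = 19 Jun 2018 | Placebo, U = 11 May 2018 | Luspatercept if re-treated, U = 19 Jun 2018 | Luspatercept if re-treated, U = 11 May 2018 |
|---|---|---|---|---|
| 6 weeks | 20 Dec 2016 | 11 Nov 2016 | 6 Jun 2017 | 28 Apr 2017 |
| 8 weeks | 6 Dec 2016 | 28 Oct 2016 | 23 May 2017 | 14 Apr 2017 |
| 12 weeks | 8 Nov 2016 | 30 Sep 2016 | 25 Apr 2017 | 17 Mar 2017 |

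For example, a placebo subject first dosed on 1 October 2016 reaches Week 48 on 2 September 2017. That is 41.4 weeks before 19 June 2018, so after the 24-week history 17.4 weeks are blank. With a first dose on 1 January 2017 the figure is 28.3 − 24 = 4.3 weeks. With 4 April 2017 it is zero, because 15.0 weeks is less than 24.

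**Partly blank 12-week windows.** Suppose the true transfusion rate is unchanged and evenly spread. The blank days needed for a false response are max(f, 2/B) × 84, where f is 0.33 or 0.50 and B is baseline units per 12 weeks.
- B = 6: 2/6 × 84 = 28 days for the 33% criterion; 0.50 × 84 = 42 days for the 50% criterion.
- B = 3: 2/3 × 84 = 56 days for both.

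At B = 6, a false 33% response in a placebo returner therefore needs a first dose by U − 336 − 168 − 28 days, which is 3 January 2017.

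**Effect per subject.** With the planned 200 and 100 subjects, one false responder adds 1/200 = 0.5 point on luspatercept or 1/100 = 1 point on placebo.

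**Who is not affected.** For a subject who never returns, last dose + 20 days lies inside last dose + 63 days. The primary and key secondary intervals end at Day 169 and Day 337, inside collection to Week 48, and SAP 10.2 and 10.3 rule out further analysis of them.

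**The case against.** **The placebo cutoff can be read otherwise.** The cross-over sentence may be only a cap that removes post-cross-over data. SAP 10.5.2 gives the final-CSR cutoff as the earliest of death, study discontinuation and last dose + 20 days, without naming an arm. Applied to the last placebo dose, that removes the gap. This stands as a possible reading, but Section 10 does not state it, and its literal wording gives the wrong result.

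**Some of the gap is recorded.** This stands: the last 24 off-drug weeks before entry are captured for placebo returners, so only early enrollees who stopped and came back can have blank weeks.

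**Protocol 8.1.1 extends reporting.** It says that blood products "used from 24 weeks prior to first dose of IP until the End of Study visit must be reported on the eCRF". That conflicts with Table 3 and with the SAP's own account of what was collected, so it cannot be relied on to fill the gap.

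**Luspatercept return is doubtful.** Protocol 3.1.4 says that subjects who stopped for non-safety reasons "may access the Open-label Phase and be re-treated with luspatercept after consultation with Sponsor Medical Monitor". The same section also requires luspatercept subjects not to have discontinued the double-blind phase. Protocol 3.1.5 keeps those in follow-up there, and SAP 4.1 describes only non-discontinuers entering. The objection stands: no luspatercept returners can be presumed.

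**Stronger inferences.** A reader might infer that re-treated luspatercept subjects inflate that arm by several points, or that the bias favours luspatercept. The documents give no count of returners in either arm, and zero is compatible with the SAP. The 281 randomized by 4 April 2017 helps with dating only; it is not the number at risk. Nor does a subject who completed 48 weeks and declined long-term treatment clearly fit the re-treatment clause, which covers discontinuation during the double-blind Treatment Period.

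**The endpoints are lower in the hierarchy.** They sit outside the gatekeeping sequence and were reported once in the primary CSR. This limits the consequence but does not make a false responder acceptable.

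**Conclusion.** The defect holds as a gap in the final-CSR rules: taken literally, they can score uncollected weeks as zero units. The documented route is discontinued placebo subjects who entered the Open-label Phase. The first-dose dates for this route assume entry no earlier than 19 June 2018 and, as the most exposed case, collection ending at Week 48. Luspatercept subjects are exposed only if re-treatment occurred.

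The effect is known only per subject. The total and its net direction cannot be determined: placebo has the clearer route back but partial capture, while any luspatercept returner would have no retrospective capture. It would be wrong to say that returners are certain to be misclassified, that their whole gap went unrecorded, or that the trial's main result is in doubt.

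**What to change.** In SAP Section 10, with cross-references in 10.5.1, 10.5.7, 10.5.9 and 10.5.10:

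1. Count a rolling or fixed interval only if every day in it lies in a period when transfusions were being collected for that subject.
2. Exclude uncollected days from response durations, from the study-duration denominator in 10.5.7, and from exposure in the transfusion-frequency models.
3. Set the placebo cutoff at the earlier of last placebo dose + 20 days and cross-over.

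Items 1 and 3 are not interchangeable. Ending the window after the first course would discard all open-label data for any re-treated luspatercept subject, whereas counting collected days keeps them.

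Reconcile Protocol 8.1.1 with Table 3, footnote 24, on when transfusion reporting ends. Reconcile the statements in Protocol 3.1.4, Protocol 3.1.5 and SAP 4.1 on whether discontinued luspatercept subjects could enter the Open-label Phase. Report how many subjects in each arm returned after stopping.

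The cost is some SAP wording and one date variable per subject. A little off-drug follow-up is lost, including the retrospective placebo history as efficacy data.

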10.5.10 Post-baseline Transfusion Event Frequency

The post-baseline transfusion event frequency during the individual 12-week interval (week 1-12, week 13-24, week 25-36, week 37-48, week 49-60, etc. until the maximum available 12-week interval) and the overall post-baseline transfusion frequency will be analyzed using negative binomial regression with the geographical regions defined at randomization and baseline transfusion frequency (12 weeks on or prior to Dose 1 Day 1) in the regression model. The p-value will be provided from the model. For the definition of transfusion events, if multiple transfusions happen on the same date, they are counted as one event; if multiple transfusions happen on two consecutive dates, they are counted as one event; if multiple transfusions happen on three consecutive dates, they are counted as two events. A similar analysis will be conducted for any 24-week interval with a comparable 24-week baseline (24 weeks on or prior to Dose 1 Day 1).

The same summary statistics for transfusion event frequency will be repeated for erythroid responders (33% and 50% during any 12-week/24-week interval respectively).

10.5.11 Pre-transfusion Hemoglobin Change from Baseline

To estimate the change of pre-transfusion hemoglobin value after dosing within each 12-week interval (week 1-12, week 13-24, week 25-36, week 37-48, week 49-60, etc.), summary statistics for the baseline, post-baseline and change from baseline pre-transfusion hemoglobin values will be provided by treatment group. The number and percentage of subjects meeting selected change category (Decrease ≥ 2 g/dL, Decrease ≥ 1.5 -<2 g/dL, Decrease ≥ 1 -<1.5 g/dL, Decrease ≥ 0.5 -<1 g/dL, Decrease >0 -<0.5 g/dL, Increase ≥ 0 -<0.5 g/dL, Increase ≥ 0.5 -<1 g/dL, Increase ≥ 1 -<1.5 g/dL, Increase ≥ 1.5 -<2 g/dL and Increase ≥ 2 g/dL) will be provided separately. Baseline pre-transfusion hemoglobin is defined as mean of all documented pre-transfusion hemoglobin values collected during the 24 weeks prior to Dose 1 Day 1. Post-baseline pre-transfusion hemoglobin is

defined as mean of all documented pre-transfusion hemoglobin values collected during each 12-week interval. The same summary statistics and categorized pre-transfusion hemoglobin change from baseline analyses will be repeated for erythroid responders (33% and 50% at week 13-24), non-responders (33% and 50% at week 13-24), and responders (33% and 50% during any 12-week interval) respectively. A similar analysis will be conducted for each 24-week interval.

In addition, hemoglobin values from central lab will be summarized in the same way by 12-week interval. Only hemoglobin measurements on the same day as transfusion or 14 days after transfusion date will be included, i.e., if a hemoglobin measurement occurs within 14 days after any transfusion, the hemoglobin value will be excluded from analysis.

